### **Statistical Analysis Plan**

T tests will be used to compare variables (e.g. force) before and after physical therapy, with post-hoc testing (Tukeys) to determine differences. A p value of less than 0.05 will be taken as indicating statistical significance for comparisons.

PROTOCOL TYPE

0 u  
co

Which IRB

Medical  NonMedical

Protocol Process Type

Exemption  
 Expedited (Must be risk level 1)  
 Full

**IMPORTANT NOTE: Once you have saved your choices under "Which IRB" and "Protocol Process Type", you will not be able to change your selections. If you select the wrong IRB Type and/or your application is deemed eligible for a different Protocol Process Type, it may be necessary to create a new application.**

Please see below for guidance on which selections to make, and/or go to ORI's "[Getting Started](#)" web page. If you still have questions about which IRB or Protocol Process Type to choose, please contact the Office of Research Integrity (ORI) at [contact] **prior** to saving your selections.

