The objective for this study is to determine if daily exercise using All-Stim 2 stimulation of quadriceps muscles will increase leg strength and improve outcomes (duration of hospitalization, long term mobility, long term disability) for mechanically ventilated MICU patients. We plan to randomize patients accepted into this protocol to administration of either sham exercise (i.e. placement of All-Stim 2 units on the legs for 30 minutes a day without activation of the electrical stimulation program) or active exercise (placement of All-Stim 2 electrodes on both legs and stimulating quadriceps muscles to rhythmically contract for 30 minutes a day). The two groups (sham and active exercise) will be treated for 30 minutes a day for seven days. The effects of exercise on quadriceps strength will be assessed by measuring quadriceps force generation (QuadTw) in response to magnetic stimulation of the femoral nerves. The QuadTw assessment will be made immediately before institution of sham or active exercise and will be repeated one day after the conclusion of the seven day training regimen. Chart review and patient follow-up will be used to determine if this treatment regimen has an impact on clinical outcome measures, i.e. duration of hospitalization, long term mobility, long term disability.

**Study Design:** Describe the study design (e.g., single/double blind, parallel, crossover, etc.). Indicate whether or not the subjects will receive placebo medication at some point in the research procedures. Also, indicate whether or not the subjects will be randomized in this study. You may reference sponsor's protocol pages and attach as an appendix in the E-IRB "Additional Information" section, however, a summary paragraph must be provided in the text box below. (Including the study design table from a sponsor's protocol is helpful to IRB members.)

*Community-Based Participatory Research:* If you are conducting [community-based participatory research \(CBPR\)](#), describe strategies for involvement of community members in the design and implementation of the study, and dissemination of results from the study.

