*Research Repositories:* If the purpose of this submission is to establish a Research Repository (bank, registry) indicate whether the material you plan to collect would or would not be available from a commercial supplier, clinical lab, or established IRB approved research repository. Provide scientific justification for establishment of an additional repository collecting duplicate material. Describe the repository design and operating procedures. For relevant information to include, see the UK Research Biospecimen Bank Guidance [\[PDF\]](#) or the UK Research Registry Guidance [\[PDF\]](#)

The basic study design is to:

- (a) obtain informed consent;
- (b) measure magnetic stimulated quadriceps twitch (QuadTw) strength bilaterally;
- (c) randomize patients to treatment with either:

Sham therapy, consisting of bilateral placement of All-Stim 2 electrodes for 30 minutes a day without activation of the electrical circuitry of the unit, or

Active therapy, using the All-Stim 2 electrodes to actively produce a rhythmic quadriceps contraction for 30 minutes a day.

We plan to have a total of 24 patients in the study, with two patients randomized to active treatment for every one patient given sham treatment. As a result we anticipate the final group studied will include 14-16 active treatment patients and 6-8 sham treatment patients.

- (d) continue these regimens daily for 7 days;
- (e) remeasure magnetic stimulated QuadTw on day 8;
- (f) the research team will visit the patient until discharge and will record duration of mechanical ventilation, duration of ICU stay, and total duration of hospitalization; and,
- (g) patients will be visited by a member of the research team at 28 days after study entry to assess the distance that can be walked in 6 minutes (i.e. the 6 minute walk test) and to assess patient well being using the St. Georges Research Questionnaire (SGRQ, a commonly used and extensively validated instrument to assess patient well being).

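### The SAP tests force before versus after therapy and never compares the randomised active and sham arms, so change that would have happened anyway can pass for a treatment effect or hide one

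*Combined protocol and SAP*

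**What the plan says.** The whole Statistical Analysis Plan is two sentences. The first is "T tests will be used to compare variables (e.g. force) before and after physical therapy, with post-hoc testing (Tukeys) to determine differences". The second sets the threshold: "A p value of less than 0.05 will be taken as indicating statistical significance for comparisons". Neither mentions active, sham, arm or group.

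The design is a randomised, sham-controlled comparison. Under Objectives in the Research Description: "The objective for this study is to determine if daily exercise using All-Stim 2 stimulation of quadriceps muscles will increase leg strength and improve outcomes", and "We plan to randomize patients accepted into this protocol to administration of either sham exercise" or active exercise. Quadriceps twitch force (QuadTw) is measured twice in both arms, the second time on day 8: "The QuadTw assessment will be made immediately before institution of sham or active exercise and will be repeated one day after the conclusion". Under Study Design: "We plan to have a total of 24 patients in the study, with two patients randomized to active treatment for every one patient given sham", with the expectation that "the final group studied will include 14-16 active treatment patients and 6-8 sham treatment patients".

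No other section adds a between-arm test. Objectives says the effect on strength will be assessed by measuring QuadTw, without naming a contrast. Data and Safety Monitoring gives a board member responsibility for the statistical analysis but does not say what it is.

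**The concern.** The question is causal: does stimulation increase leg strength? A before/after change in acutely ill patients is the sum of any stimulation effect and whatever would have happened over those eight days anyway. The Background puts QuadTw in these patients at about 12 N against 38 N in healthy adults, so there is ample room for movement in either direction. Only the contrast with sham removes that shared component.

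Followed literally, the plan either leaves the sham arm unused or invites setting two within-arm p values side by side. The second is not a test of the difference between arms, and it is skewed here because the active arm is twice the size of the sham arm and so reaches p<0.05 more readily for the same change.

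The Tukey step does not rescue the plan. Tukey's procedure compares several means after an ANOVA; it does not follow a t test, and two arms need no post-hoc step.

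A before/after test also cannot be applied to length of stay, ventilation time, the 28-day walk or the SGRQ, none of which has a pre-therapy study value.

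**Working it through.** The documents contain no power or effect-size figure to reproduce, so this is an illustration of size.

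**Inputs from the documents.** Arms of 16 and 8 (24 at 2:1, the top of the stated ranges); alpha 0.05, taken as two-sided; QuadTw 12 + 4 N in Background, with 4 N read as an SD although it is not labelled.

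**Assumed, not in the documents.** Pre/post correlation ρ of 0.5 to 0.9, and a common change of 1 to 3 N in both arms. The before/after t test is taken as paired.

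**Formulas.** SD of change = 4√(2(1−ρ)). Paired test: noncentrality = δ√n / SD of change, on n−1 df. ANCOVA: residual SD = 4√(1−ρ²), standard error = residual SD × √(1/16+1/8), on 21 df.

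**1. No treatment effect, both arms gain 2 N, ρ = 0.7.** SD of change = 4√0.6 = 3.10 N.
- Active: 2×√16/3.098 = 2.58 on 15 df, significant in 67.5% of trials.
- Sham: 2×√8/3.098 = 1.83 on 7 df, significant in 35.2%.
- Active significant and sham not: 0.6752 × (1 − 0.3515) = 43.8%.
- Baseline-adjusted comparison of arms: about 5% by simulation.

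**2. Range, still with no treatment effect (16 and 8).**

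| ρ | SD of change (N) | Active significant, +2 N | Sham significant, +2 N | Active only, +1 N | Active only, +2 N | Active only, +3 N |
|---|---|---|---|---|---|---|
| 0.5 | 4.00 | 46% | 23% | 14% | 36% | 44% |
| 0.7 | 3.10 | 68% | 35% | 20% | 44% | 33% |
| 0.8 | 2.53 | 84% | 49% | 26% | 43% | 18% |
| 0.9 | 1.79 | 99% | 77% | 40% | 22% | 2% |

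The active-only pattern falls at the lower right because sham becomes significant too. The active before/after test is then wrong almost every time.

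**3. A real benefit hidden (sham loses 3 N, active holds, ρ = 0.7).** The active arm's true mean change is zero, so its test rejects in 5% of trials. For ANCOVA, residual SD = 4√0.51 = 2.86 N and standard error = 2.857 × 0.433 = 1.237 N. Noncentrality is 3/1.237 = 2.43, giving 64% power in closed form. Simulation, which includes the cost of estimating the baseline slope, gives 62%.

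**4. Difference between arms detectable with 80% power (ρ = 0.7).** 5.1 N on day-8 values alone, 3.9 N on change scores, 3.6 N with ANCOVA.

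**5. Tukey on the four arm-by-time cells.** If the two measurements on a patient are treated as independent, the variance assigned to a single patient's before/after difference is 2×16 = 32 N², against 2×16×(1−0.7) = 9.6 N² when the pairing is used. None of the six pairwise comparisons is the difference in change between arms. The day-8 active-versus-sham pair ignores baseline, so before any multiplicity penalty it has the 5.1 N limit in step 4.

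**The case against.** The strongest reply is that the SAP sentence is unclear rather than wrong. It does not say paired, does not rule out a between-arm test, and its mention of Tukey may mean the authors pictured an ANOVA over four arm-by-time cells that would include active versus sham. That is possible, but no arm, factor or interaction is named, and such an ANOVA would have the faults in step 5. Reading two within-arm p values together is likewise one way the plan could be applied, not something it states.

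Several qualifications stand:

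- The 44% is the top of the 14–44% range over ρ 0.5–0.8 and gains of 1–3 N.
- The active arm's advantage in reaching p<0.05 depends on the size of the change. At ρ = 0.7 the ratio of active to sham power is 1.92 at 2 N, 1.46 at 3 N and 1.14 at 4 N.
- Smaller arms change the figures. At 14 and 6, ANCOVA power for 3 N is about 51% (ρ = 0.7), and the false active-only pattern reaches about 51% (2 N, ρ = 0.8).
- A two-sample test of change would also be valid; ANCOVA is preferred for precision.
- Ventilation time is listed under Study Design and Hospital Outcomes, not in the objective. Family-reported pre-hospital ambulation gives a rough earlier measure of mobility, though not a baseline walk test or SGRQ.

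None of these supplies the missing comparison.

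**Conclusion.** The concern holds. The only contrast the SAP states does not answer the trial's own question, and nothing elsewhere in the documents corrects it. It can credit stimulation with recovery shared by both arms, and it can miss a benefit that consists of preventing decline. With SD 4 N, ρ 0.7 and arms of 16 and 8, the first error occurs in 68% of trials for a shared 2 N gain (44% if sham must also be non-significant). In the second case the active before/after test finds a 3 N benefit in 5% of trials, against about 62% for ANCOVA. These sizes rest on an unlabelled SD and on a correlation and common change that the documents do not give; the direction of both errors does not. This must be fixed before the data are analysed. The correct comparison will still have limited power at this sample size, and the plan should say so.

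**What to change.** Replace the first SAP sentence with wording such as: *The primary analysis compares day-8 QuadTw between active and sham by ANCOVA adjusting for baseline QuadTw, in all randomised patients with a day-8 value, in the arm assigned. The adjusted difference and its 95% confidence interval will be reported. Within-arm changes are descriptive.*

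Delete the Tukey step. State how the two legs are combined, since Research Procedures measures each and gives no rule; the mean of both legs per patient is a simple choice. Report by arm how many patients lack a day-8 value and why, because deaths and transfers are expected. Compare the remaining outcomes between arms as supportive results with confidence intervals.

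The cost is SAP wording: baseline QuadTw is already scheduled for every patient, and no new data or patients are needed. Because 15 of 24 patients are already enrolled, make the change as a dated amendment before results by arm are examined, and record whether anyone has seen them.

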We are in the process of completing a study at the University of Kentucky that indicates critically ill patients have severe respiratory and limb muscle weakness. To date, this work has found that the average patient in the University of Kentucky MICU has a diaphragm pressure generation (Pdi) in response to phrenic magnetic twitch stimulation of only 8.5 + 3 cm H2O, compared to a normal value of 36 cm H2O for healthy adults. As a result, these patients have an average diaphragm strength that is only 24% of normal. In addition, we measured the strength of the largest leg muscle, the quadriceps in the thigh, and found that this muscle only generates an average twitch force of 12 + 4 Newtons in mechanically ventilated patients, compared to an average value of 38 Newtons for healthy adult controls. As a result, the leg strength of these patients is only 32% of normal. Our work also indicates that weakness is correlated with poor outcomes, with the weakest patients having the highest mortality, the longest duration on mechanical ventilation, and the longest ICU stays. Importantly, we found that weakness was a better predictor of patient outcomes than indices of lung disease (PaO2/FiO2 ratios, lung compliance, airway resistance), with weak patients having the same poor outcomes whether they have near normal or severe lung function. In addition, recent work by [name] has shown that leg muscle weakness can persist for as long as five years after ICU discharge, with this prolonged weakness contributing greatly to long term morbidity and disability (1, 2).

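### The SAP names no active-versus-sham comparison and no covariate for the clinical outcomes, although the protocol reports weakness as prognostic and lists baseline QuadTw before randomisation

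*Combined protocol and SAP*

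**What the plan says.** The Statistical Analysis Plan is two sentences long. It states that "T tests will be used to compare variables (e.g. force) before and after physical therapy" and names Tukey post-hoc testing for locating differences. Its second sentence sets the threshold: "A p value of less than 0.05 will be taken as indicating statistical significance for comparisons". No regression model, covariate, stratification factor or active-minus-sham contrast appears there or elsewhere in the documents.

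The Objectives section says that chart review and follow-up will be used to judge whether the treatment affects clinical outcomes: length of hospitalisation, long-term mobility and long-term disability. The Study Design and Hospital Outcomes sections add duration of ventilation or time to weaning, ICU stay and a 6-minute walk at 28 days.

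The Background reports the investigators' own finding that the weakest patients had the highest mortality, the longest ventilation and the longest ICU stays, and that "weakness was a better predictor of patient outcomes than indices of lung disease". Study Design step (b) is to "measure magnetic stimulated quadriceps twitch (QuadTw) strength bilaterally"; randomisation is step (c). On size, the plan is 24 patients allocated 2:1 in favour of active treatment, and the Study Design expects that "the final group studied will include 14-16 active treatment patients and 6-8 sham treatment patients".

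**The concern.** The trial intends to draw conclusions about clinical outcomes, but the SAP does not say how the arms will be compared on them. The stated before-after test cannot do it: weaning time, ICU stay, hospital stay and the day-28 walk have no value before therapy.

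Once a between-arm comparison is written, the next question is whether it uses the one baseline measurement that the protocol itself presents as prognostic. With about 16 and 8 patients and no stratification described, one arm can easily start weaker by chance. If weakness drives the outcome, that imbalance enters an unadjusted estimate, where it can look like a treatment effect or hide one. If the model is left open until the data are seen, the choice of whether to adjust can also follow the result.

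**Working it through.** **Inputs from the documents.** N = 24 at 2:1, which is 16:8; the stated ranges go down to 14:6. Baseline QuadTw in ventilated patients is 12 N with a spread of 4 N (Background). Alpha is 0.05.

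**Assumptions.** The 4 N is an SD. Testing is two-sided. r, the absolute correlation of baseline QuadTw with an outcome, is not given, so a range is shown. The outcome is complete and roughly normal. An effect of 1 outcome SD is used for illustration. The plan gives no power, target effect or outcome SD, so there is no sample-size calculation to reproduce; one can only confirm that 24 at 2:1 is 16:8.

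**Step 1. Chance imbalance.** The SD of the arm difference in mean baseline QuadTw, in baseline SD units, is √(1/n₁ + 1/n₂).
- 16:8: √(1/16 + 1/8) = 0.433, or 4 × 0.433 = 1.73 N. P(|difference| > 0.5 SD) = 2[1 − Φ(0.5/0.433)] = 25%.
- 14:6: √(1/14 + 1/6) = 0.488, or 1.95 N. The same probability is 31%.

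**Step 2. What an imbalance does to one unadjusted result.** The expected shift is r × imbalance. An imbalance of 0.5 SD shifts the estimate by 0.15, 0.25 or 0.30 outcome SD at r = 0.3, 0.5 or 0.6. Simulated false-positive rates at 16:8 with no treatment effect:

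| r | Unadjusted, imbalance > 0.5 SD (25% of trials) | Unadjusted, other 75% | Unadjusted, all trials | Adjusted, imbalance > 0.5 SD |
|---|---|---|---|---|
| 0.3 | about 7% | 4.4% | about 5% | about 5% |
| 0.5 | about 10% | 3.4% | about 5% | about 5% |
| 0.6 | about 12% | 2.7% | about 5% | about 5% |

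**Step 3. Precision and power.** The expected ratio of adjusted to unadjusted variance is (1 − r²)(n − 3)/(n − 4). At n = 24 the second factor is 21/20 = 1.05.

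| r | Variance ratio, 16:8 | Equivalent unadjusted N (24/ratio) | Power at 1 SD, 16:8 |
|---|---|---|---|
| unadjusted | 1 | 24 | 60% |
| 0 | 1.05 | 22.9 | 58% |
| 0.2 | 1.01 | 23.8 | 59% |
| 0.3 | 0.96 | 25.1 | 62% |
| 0.5 | 0.79 | 30.5 | 70% |
| 0.6 | 0.67 | 35.7 | 77% |

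At 14:6, power is 49% unadjusted and 50%, 58% or 65% adjusted at r = 0.3, 0.5 or 0.6. Break-even is r = √(1/(n − 3)): √(1/21) = 0.22 at 16:8 and √(1/17) = 0.24 at 14:6.

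**Step 4. Which outcomes the prognostic statement covers.** The Background names mortality, ventilation duration and ICU stay. It does not name hospital stay or walking distance. It follows data on both the diaphragm and the quadriceps, speaks of weakness in general and gives no coefficient.

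**Step 5. Whether the durations are complete.** Hospital Outcomes records transfer to a long-term facility (LTAC) or death for patients who are not weaned. For them time to weaning is not observed. Early death also shortens ICU and hospital stay, so a short stay is not always a good result. Patients who have died cannot do the day-28 walk.

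**The case against.** The strongest reply is that the SAP never says the clinical outcomes will be compared without adjustment. Its sentence is a before-after test with force as the example, and the Data and Safety Monitoring section leaves the appropriate analysis to a board member with a background in statistics. This stands. A reader might infer that an unadjusted between-arm t test is planned, but the documents do not say so. The documented gap is that no between-arm analysis is specified at all.

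Second, an unadjusted randomised comparison is valid: it is unbiased on average and keeps its 5% level over all trials. This also stands. The raised rates apply only to the imbalanced quarter of trials and are offset by lower rates in the rest. They still matter to a team that runs one trial and will see its own imbalance.

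Third, the gain depends on an r that the documents do not give. That is correct: at r of 0.2 or less adjustment does not help, and material gains need r near 0.5.

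Fourth, choosing a covariate is secondary to specifying the comparison itself. That is fair as to order, but both can be settled in the same paragraph of the SAP.

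**Conclusion.** The point holds in this form: the SAP specifies neither a between-arm comparison nor a covariate for the clinical outcomes, and it leaves unused a pre-randomisation measurement that the protocol's own evidence supports as prognostic. At 16:8 about one trial in four (31% at 14:6) would have a baseline imbalance above 0.5 SD. In those trials an unadjusted test would be wrong about 7%, 10% or 12% of the time at r = 0.3, 0.5 or 0.6. Power at 1 SD would go from 60% to 62%, 70% or 77% with adjustment.

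Two stronger readings are not supported. One is that precision is certainly lost without adjustment; that requires r above about 0.22, and r is unknown. The other is that the protocol's evidence shows that a weaker arm will stay longer in hospital and walk less; neither outcome is named in that evidence, and quadriceps weakness is not separated from diaphragm weakness.

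The figures rest on the 4 N being an SD, two-sided testing, an assumed r, and complete, normal outcomes. They are a guide only for durations cut short by death or transfer. The change should be made; confidence is moderate because r is not given.

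**What to change.** State in the SAP that the active-versus-sham comparison of time to weaning (or ventilation duration) and ICU stay is adjusted for baseline QuadTw, the mean of the two legs measured before randomisation, as the single prespecified covariate. Apply the same to hospital stay and the 6-minute walk, noting that documentary support is weaker there. Show the unadjusted estimate beside the adjusted one, and say in advance which is the main result.

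For the durations, use a method that accounts for death and LTAC transfer, for example a time-to-event model with death as a competing event and a stated rule for transfers. A plain linear model on log duration does not do this. Report by arm how many patients have no day-28 walk, and why.

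No new measurement is needed, and with 15 of 24 patients enrolled at this renewal the wording can still be fixed before analysis. Writing the competing-event and missing-walk rules takes more work than naming the covariate. The statistical price is one degree of freedom: if r is zero, variance rises by about 5% (21/20) and power at 1 SD is about 58% instead of 60%.

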**Hospital Outcomes:** After recruitment into studies, electronic hospital records will be reviewed twice a week to determine the time from the point of initial study measurements to successful weaning from mechanical ventilation (defined as remaining off all mechanical ventilation for more than 4 days). Alternative outcomes that will be recorded, for patients that are not weaned from mechanical ventilation, include transfer to a chronic facility for long term weaning from mechanical ventilation (i.e. an LTAC) or death. Deaths will be further subclassified as death due to withdrawal of care and death due to progression of disease. We will also record total ICU stay, total days of hospital stay, and incidence of recurrent respiratory failure, defined as a requirement for reintubation either during the initial hospitalization or at any time out to day 28 after entry into the study. We will also record hospital readmission rates.

**Follow-up Visit (28 days).** At follow-up visits we will assess the distance walked in 6 minutes and we will ask patients if they have returned to work (either full time or part time). We will also have patients fill out the St. Georges respiratory questionnaire (SGRQ) on return visits. This questionnaire evaluates patient's perceptions about their respiratory health, including their assessment of the ability to perform simple tasks of daily living. The PI and/or [name] will visit the patient's domicile (or other site of habitation) to obtain these assessments.

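### The SAP treats any comparison with p<0.05 as significant, names no primary outcome and does not adjust across outcomes

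*Combined protocol and SAP*

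**What the plan says.** The Statistical Analysis Plan is two sentences long. The first names the test: "T tests will be used to compare variables (e.g. force) before and after physical therapy, with post-hoc testing (Tukeys) to determine differences". The second sets the criterion: "A p value of less than 0.05 will be taken as indicating statistical significance for comparisons". There is no list of tested outcomes, no ordering of tests, no sidedness and no adjustment across outcomes. No outcome is labelled primary anywhere in the supplied text.

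Under Objectives, the aim is to find out whether daily stimulation "will increase leg strength and improve outcomes (duration of hospitalization, long term mobility, long term disability) for mechanically ventilated MICU patients". That is four domains: strength, hospital stay, mobility and disability. The same section says that chart review and follow-up will be used to decide whether treatment affects the clinical outcomes.

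The other outcomes are under Research Procedures. Hospital Outcomes starts from time to "successful weaning from mechanical ventilation (defined as remaining off all mechanical ventilation for more than 4 days", with transfer to a long-term facility (LTAC) or death recorded for patients who are not weaned. It continues: "We will also record total ICU stay, total days of hospital stay, and incidence of recurrent respiratory failure", and then adds readmission. Follow-up Visit (28 days) says: "At follow-up visits we will assess the distance walked in 6 minutes and we will ask patients if they have returned to work", and adds the SGRQ.

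Study Design plans 24 patients, allocated 2:1 to active or sham treatment.

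**The concern.** A single 5% threshold that covers every comparison keeps the error rate at 5% per test, not for the trial. When several outcomes bear on one objective and none is designated in advance, the chance that something crosses the line grows with the number of tests. The one multiple-comparison method named does not help, because Tukey's procedure compares group means within one outcome.

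With 24 patients, a single chance result on, say, ICU days or walk distance could be reported as evidence that stimulation works. Nothing in the plan would mark it as one of several tries. The protocol also uses the clinical outcomes for inference, and p<0.05 is the only criterion it supplies.

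**Working it through.** The documents give no familywise error rate, power or sample-size derivation, so there is no figure of theirs to reproduce.

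**Inputs**
- Threshold per comparison: 0.05, unadjusted (SAP).
- Sidedness: not stated. Assumption: two-sided, so 0.025 in the direction of benefit.
- Outcomes: 4 domains (Objectives), or about 11 collected measures. Six are durations, distances or scores: QuadTw, time to weaning, ICU days, hospital days, 6-minute walk and SGRQ. Five are yes/no: LTAC transfer, death, recurrent respiratory failure, readmission and return to work.
- Group sizes: 16 active and 8 sham (24 patients at 2:1, Study Design).
- Assumption: each outcome gets a valid active-versus-sham test. The SAP does not say this.

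**Step 1. Independent tests, no treatment effect.** For k tests, the chance of at least one p<0.05 is 1 − 0.95^k in either direction and 1 − 0.975^k in the direction of benefit.

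| Outcomes tested | Either direction | Benefit only |
|---|---|---|
| 1 | 5.0% | 2.5% |
| 4 (stated domains) | 1 − 0.95^4 = 18.5% | 1 − 0.975^4 = 9.6% |
| 6 (non-binary only) | 1 − 0.95^6 = 26.5% | 1 − 0.975^6 = 14.1% |
| 11 (all) | 1 − 0.95^11 = 43.1% | 1 − 0.975^11 = 24.3% |

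**Step 2. Upper limit under any dependence, 11 tests.** Either direction: 11 × 0.05 = 55%. Benefit: 11 × 0.025 = 27.5%. So 43.1% is the value under independence and not a bound.

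**Step 3. Positive correlation.** Simulation of 11 equally correlated normal outcomes, two-sample t tests, 16 versus 8 patients, 40,000 trials per setting. The correlations are assumed; the documents give none.

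| Correlation | Either direction | Benefit only |
|---|---|---|
| 0 | 42.9% | 24.2% |
| 0.3 | 37.8% | 19.4% |
| 0.5 | 31.2% | 15.8% |
| 0.7 | 23.6% | 11.9% |
| 0.9 | 13.7% | 6.9% |

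**Step 4. Exact tests for the five binary outcomes.** With Fisher's exact test at 16 versus 8 and assumed event rates of 10% to 50%, the true either-direction size per test is 0.9% to 2.8%. Combined with six independent 5% tests, the either-direction rate is 1 − 0.95^6 × (1 − 0.009)^5 ≈ 30% to 1 − 0.95^6 × (1 − 0.028)^5 ≈ 36%. In the direction of benefit it is about 18% to 20%, if fewer events count as benefit for all five outcomes. Return to work runs the other way, which lowers the bottom of that range slightly.

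**The case against.** The strongest reply is that the SAP never says it will test 11 outcomes. It names before/after t tests with force as the example, and QuadTw is the only listed outcome with both values: "The QuadTw assessment will be made immediately before institution of sham or active exercise", and again on day 8. The hospital and follow-up measures are described as recorded or assessed, with no test attached. This stands, and it is why every rate above is conditional. It does not remove the point. The SAP speaks of variables in the plural and of comparisons without limit, and Objectives says that follow-up will settle whether the clinical outcomes are affected.

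A second reply is that QuadTw is plainly the lead outcome: the project title is about limb muscle strength, strength comes first in the objective, and force is the SAP's example. That is fair, and it makes the choice of primary easy. It does not restrict the significance rule to that outcome.

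A third reply is that 11 independent 5% tests are unrealistic. Ventilator, ICU and hospital days overlap, death and LTAC transfer are tied to weaning, and five outcomes are binary. This also stands; steps 3 and 4 show the reduction.

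A reader might also infer that the objective counts a gain on any one outcome as success. The text does not support that. It joins strength and the other outcomes with an and, and lists three domains beside strength. Death, LTAC transfer, reintubation, readmission, ICU days and weaning time are not in it.

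**Conclusion.** The point holds in a conditional form. The threshold is unadjusted and no outcome is primary. If the rule is applied to active-versus-sham tests at two-sided 0.05, the false-positive rate under independence is 18.5% for the four stated domains and about 43% for all 11 outcomes. For apparent benefit it is 9.6% and about 24%, against nominal rates of 5% and 2.5%. Even the narrow count of four is nearly four times nominal (18.5/5 = 3.7; 9.6/2.5 = 3.9). With 11 outcomes and assumed correlations of 0.5 to 0.3, the benefit rate is about 16% to 19%.

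A reader might conclude that a useless treatment has up to a 43% chance of a significant benefit. The documents do not support that. The 43% includes differences in favour of sham, it is not an upper limit, and reading it as benefit would require one-sided tests at 0.05, which the SAP does not state.

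These rates also take between-arm tests for granted. A before/after t test within an arm can reach significance from natural change over eight days. That is a separate weakness, and these figures do not measure it.

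**What to change.** Before any outcome is examined by arm, revise the SAP as follows.

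- Name one primary test: the active-versus-sham difference in day-8 QuadTw at two-sided 0.05. State how the two legs give one value per patient, because Quadriceps Twitch measures both and gives no rule for combining them.
- Restate the significance sentence so that p<0.05 supports a confirmatory claim for that test only.
- List the remaining outcomes as secondary or exploratory, and report each as an active-minus-sham estimate with a 95% confidence interval.

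The cost is wording: no added patients, visits or procedures. The continuation review reports 15 of 24 patients enrolled and recruitment stopped because of COVID-19, so the change can be dated before the remaining patients enter. The small downside is that a nominal p<0.05 on a secondary outcome no longer counts as confirmed benefit. If the investigators want confirmatory claims on more outcomes, an adjustment is the alternative. Bonferroni over 11 tests uses 0.05/11 = 0.0045 each and holds the either-direction rate at 4.9% under independence, but with 24 patients that leaves little power. This is a cheap improvement.
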